APPENDIX A. SCHEDULE OF EVENTS

Study Procedures	Screening	Day 1	Week 2	Week 4	Week 8	Week 12	FU Visit
Informed Consent	X						
Incl/Excl Criteria	X						
Demographics	X						
Medical History	X						
Concomitant Meds	X	X	X	X	X	X	X
Physical Exam ^a	X						X
Neurological Exam	X						X
Height	X						
Weight & BMI	X	X	X	X	X	X	X
12-Lead ECG	X			X			X
Vital Signs	X ^b	X	X	X	X	X	X
Clinical Safety Labs ^c	X	X	X	X		X	X
Pregnancy Test ^d	X						X
PK Sample ^e		X	X	X	X	X	
SVC	X	X	X	X	X	X	X
Muscle Strength	X	X	X	X	X	X	X
ALSFRS-R	X	X	X	X	X	X	X
Voice recording	X	X	X	X	X	X	X
Fine Motor Skills ^f	X	X	X	X	X	X	X
ALSAQ-5	X	X	X	X	X	X	X
Health Economic Outcomes Measurements		X	X	X	X	X	X
Ashworth Scale	X	X	X	X	X	X	X
Falls Assessments		X	X	X	X	X	X
Study Drug Dosing		X	X	X	X	X	
AE/SAE Evaluations		X	X	X	X	X	X
BDI-Fast Screen	X	X	X	X	X	X	X

a Complete physical examination at Screening Visit, abbreviated physical examination at FU visit

b Temperature only at Screening

b Oral temperature only at Screening

c TSH only at Screening and Follow-Up Visit

d Only for females of childbearing potential

d Serum pregnancy test only for females of childbearing potential

e PK sampling on Day 1 visit, Week 2 visit, Week 4 visit, Week 8 visit, and Week 12 visit; refer to Table 3 in the protocol

f If the device is suitable for use in that region

Schedule of Events for Home Testing

SVC*	To be done every Saturday independent of day of first dose
Voice recording	To be done every Saturday independent of day of first dose

*if the device is suitable for use in that region

APPENDIX B. ANALYSIS VISIT WINDOWS

Analysis Visit Windows for SVC, Muscle Strength, ALSFRS-R, Voice Recording, Fine Motor Skills, ALSAQ-5, Vital Sign, Ashworth Scale and BDI-Fast Screen

Visit	Scheduled Day	Lower Bound	Upper Bound
Screening	<1	<1	<1
Day 1	1	1	1
Week 2	15	2	21
Week 4	29	22	42
Week 8	57	43	70
Week 12	85	71	98
Follow-up	113	99	> 99

Analysis Visit Windows for 12-lead ECG

Visit	Scheduled Day	Lower Bound	Upper Bound
Screening	<1	<1	<1
Week 4	29	1	70
Follow-up	113	71	>71

Analysis Visit Windows for Clinical Safety Laboratories

Visit	Scheduled Day	Lower Bound	Upper Bound
Screening	<1	<1	<1
Day 1	1	1	1
Week 2	15	2	21
Week 4	29	22	56
Week 12	85	57	98
Follow-up	113	99	>99

Analysis Visit Windows for PK Concentration

Visit	Scheduled Day	Lower Bound	Upper Bound
Day 1	1	1	1
Week 2	15	2	21
Week 4	29	22	42
Week 8	57	43	70
Week 12	85	71	>71

Analysis Visit Windows for Neurological Exam

Visit	Scheduled Day	Lower Bound	Upper Bound
Screening	<1	<1	<1
Follow-up	113	1	>99

Analysis Visit Windows for SVC Assessed at Home

Visit	Scheduled Day	Lower Bound	Upper Bound
Day 1	1	1	1
Week 1	8	2	11
Week 2	15	12	18
Week 3	22	19	25
Week 4	29	26	32
Week 5	36	33	39
Week 6	43	40	46
Week 7	50	47	53
Week 8	57	54	60
Week 9	64	61	67
Week 10	71	68	74
Week 11	78	75	81
Week 12	85	82	88
Week 13	92	89	95
Week 14	99	96	102
Week 15	106	103	109
Week 16	113	110	>110

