1.3. Overview of CK-2127107 Clinical Studies

Phase 1 Studies

CK-2127107 has been evaluated in five Phase 1 studies.

In a "first in human" study conducted in 35 healthy men (Study CY 5011), single oral doses of a SDD suspension (CK-2127107 ranging from 30 to 4000 mg were all well tolerated and no maximum tolerated dose was established.

In Study CY 5012, multiple dose administration of the CK-2127107 SDD suspension at 300 and 500 mg twice daily for either 10 or 17 days was well tolerated by 59 young and elderly healthy subjects and allowed the steady-state PK profile to be described.

A 4-way crossover, single dose PK/pharmacodynamic (PD) study (Study CY 5013) performed with placebo, 300 mg, 1000 mg and 3000 mg of the CK-2127107 SDD suspension demonstrated a dose- and concentration-dependent increase in the force-frequency relationship of the tibialis anterior muscle with transcutaneous electric stimulation of the deep fibular nerve.

Another study in 25 healthy men (Study CY 5014) was conducted to evaluate the relative oral bioavailability of a suspension of the crystalline form of CK-2127107, CK-2127107 active pharmaceutical ingredient (API), to the CK-2127107 SDD suspension dosed at 300 and 1000 mg.

Lastly, in Study CY 5015, the PK of a tablet formulated with CK-2127107 API was compared to CK-2127107 API suspension and found to have adequate bioavailability for use in future studies. The food effect of the tablet was also evaluated in Study CY 5015.

The terminal half-life ($t_{1/2}$) of CK-2127107 was generally around 12 hours with a time to maximum concentration (t_{max}) of 2-3 hours. The increase in exposure was largely dose-proportional although exposure was more variable at doses ≥ 3000 mg. There were no observed differences in PK parameters between young and elderly subjects but mean exposure was

slightly higher in women vs. men. A food effect was demonstrated with 2.6- and 1.6-fold increases in C_{max} and AUC_{∞} , respectively, following administration of the tablet formulation (500 mg as 2 x 250 mg tablets) with a high fat meal.

Exposure (C_{max} and AUC) to the inactive metabolite, CK-2127106, was higher after multiple doses of CK-2127107 compared to single doses. The geometric mean half-life of CK-2127106 ranged from 25.4 to 39.3 hours. Maximum concentrations (C_{max}) and area under the concentration-time curve (AUC) values increased somewhat greater than dose-proportionally following multiple dosing.

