12. ALSAQ-5
13. Record Health Economic Outcomes Measures
14. AE/SAE evaluation and concomitant medication assessment (since last visit)
15. BDI-Fast Screen

Patients will receive their first dose of study drug (CK-2127107 or placebo) within 2 hours of a meal.

The following assessment will be performed after the first dose of study drug is given:

16. PK blood sample at 1 hour post-dose

Training will also be provided to the patient for the measurements patients will perform at home.

- For patients who have access to a mobile device, the application will be downloaded to the device and instructions provided as detailed in the study manual on recording voice.
- All patients will be trained in performing SVC using a portable spirometer (if the device is suitable for use in that region) as detailed in the study manual.

Home voice recordings and SVC testing will be performed by the patient weekly for the duration of the study following Day 1.

Patients will be given an adequate supply of study drug (CK-2127107 or placebo) to take twice daily for 4 weeks. A dosing diary will be provided for patients to record the date and time of twice daily study drug administration.

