5.6. Week 12 Visit

Prior to the last dose of study drug at the Week 12 Visit, the following procedures will be performed:

1. Vital signs, including heart rate, blood pressure, and respiratory rate measured after the patient has been resting for at least 3 minutes
2. Weight and calculation of BMI
3. PK blood sample
4. Clinical laboratory evaluations, including CBC and WBC with differential, serum chemistries, cystatin C and UA

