5.5.3. Study Day

If the date of interest occurs on or after the first dose date, then study day will be calculated as (date of interest – date of first dose) + 1. If the date of interest occurs prior to the first dose date, then study day will be calculated as (date of interest – date of first dose). There is no study day 0.

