5.5.4. Analysis Visit Windows

Since study visits do not always take place exactly as scheduled in the protocol, it is necessary to assign the actual observation dates to visit windows for analysis purposes.

For measurement taken prior to the first dose of study treatment, the visit window is defined as the interval of time prior to the first dose of study treatment. Measurements taken on or after the first dose of study treatment will be assigned to the next scheduled visit window.

For data collected at a scheduled post baseline visit, the visit window is assigned based on the scheduled study day of the nominal visit as collected on the electronic case report form (eCRF).

For unscheduled or early discontinuation post baseline visits, measurements taken on or after the first dose of study treatment will be assigned to a visit window using defined lower and upper bounds for each visit window. Measurements assigned in a visit window will have study day greater than or equal to the lower bound but no greater than the upper bound of the visit window. The lower bound and the upper bound for the visit windows are defined as the midpoints of the scheduled visits for all assessments (see [Appendix B](#)).

Visits are identified as the nominal visits according to the eCRFs. Each visit will be identified with the visit descriptor (eg, “Week 12”). If a patient has two or more study visits in one visit window, one record will be flagged as the “analyzed record” for that visit window.

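### The Week 12 home-SVC window (Days 82-88) runs past the planned last dose, so patients starting on a Wednesday, Thursday or Friday have their scheduled 'Week 12' home reading after treatment has ended

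*SAP*

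**What the plan says.** - **Window.** In the Appendix B table "Analysis Visit Windows for SVC Assessed at Home", the relevant row reads "Week 12 85 82 88" (scheduled day, lower bound, upper bound). Week 13 begins on Day 89, and the rows continue to Week 16.
- **Window rule.** SAP 5.5.4: "The lower bound and the upper bound for the visit windows are defined as the midpoints of the scheduled visits for all assessments".
- **Day count.** SAP 5.5.3: from the first dose on, "study day will be calculated as (date of interest – date of first dose) + 1". Day 1 is therefore the first-dose date.
- **Home test day.** SAP Appendix A: "To be done every Saturday independent of day of first dose". Protocol Appendix A adds a tolerance of ± 1 day. Protocol 5.2 has tests continuing after dosing ends: "SVC testing will be performed by the patient weekly for the duration of the study following Day 1".
- **Last dose.** Protocol 5.6 lists the clinic assessments, SVC among them, as done "Prior to the last dose of study drug at the Week 12 Visit". Protocol 5.9 puts that visit on Day 85 ± 4.
- **Half-life.** Protocol 1.3: the terminal half-life "of CK-2127107 was generally around 12 hours".
- **Record selection.** SAP 5.5.8.1 screens a home reading only against 0.5 to 1.5 times the same week's best clinic value. SAP 5.5.5 gives priority to scheduled visits, then to the reading nearest the scheduled day, with ties going to the later one. Neither refers to the last dose.

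**The concern.** A window symmetric about Day 85 looks natural, but treatment ends on Day 85. A fixed Saturday test then makes the weekday of first dose decide whether a patient's Week 12 home reading is on or off drug. This is a systematic product of the calendar, not random visit drift. For patients who complete dosing as planned, the clinic SVC is taken before the last dose, and the home reading with the same label has no such protection.

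Three sets of analyses are exposed:

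- the exploratory home change-from-baseline and home slope endpoints (SAP 2.2.4, 7.7);
- the combined home-plus-clinic model (SAP 7.9.3.2);
- the home-clinic correlation and paired t-test (SAP 7.9.3.1), where an off-drug home value may be paired with an on-drug clinic value and lost drug effect read as device disagreement.

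**Working it through.** **1. Reproduce the window.** Scheduled home days are 78, 85 and 92 for Weeks 11, 12 and 13. The midpoints are (78 + 85)/2 = 81.5 and (85 + 92)/2 = 88.5. In whole days this is 82-88, matching Appendix B. The upper end is three days past the nominal last dose.

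**2. Place the Saturday.** Day 85 is 84 days (12 whole weeks) after Day 1, so it falls on the same weekday. Days 82-88 hold exactly one Saturday. With the visit on Day 85:

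| First dose | Saturday in window | Days after last dose |
|---|---|---|
| Monday | 83 | on drug |
| Tuesday | 82 | on drug |
| Wednesday | 88 | 3 |
| Thursday | 87 | 2 |
| Friday | 86 | 1 |

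**3. Share off drug.** The weekday distribution of first doses is not in the documents, so each figure is conditional. The denominator is patients with a Week 12 home value.

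- Even Monday-Friday starts, Saturday tests, visit on Day 85: 3/5 = 60%.
- Same starts, visits spread equally over the allowed weekdays within ± 4 days: still 60% on average, with gaps of 1-5 days.
- Same starts, visit on Day 85, all tests on Friday 3/5 = 60%; all on Sunday 2/5 = 40%; even over Friday-Sunday 8/15 = 53%.
- Starts even over seven days: 3/7 = 43%.
- Illustrative uneven Monday-Friday mixes: weights 0.4, 0.3, 0.1, 0.1, 0.1 give 30%; weights 0.1, 0.1, 0.2, 0.3, 0.3 give 80%.

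**4. Drug remaining.** The fraction is 0.5^(24 × days/12): 0.25 after 1 day, 0.0625 after 2 and 0.0156 after 3, or about 25%, 6% and 1.6%.

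**5. Dilution of the Week 12 home change endpoint.**

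- Effect persists off drug: no loss.
- Effect proportional to concentration, even Monday-Friday starts, Saturday tests, Day 85 visit: retained (1 + 1 + 0.0156 + 0.0625 + 0.25)/5 = 2.328/5 = 0.466, a loss of about 53%.
- Same, with all tests on Sunday (Thursday starters 3 days late, Friday starters 2): retained (3 + 0.0156 + 0.0625)/5 = 0.616, a loss of about 38%.

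**6. Dilution of the home slope.** Assume 12 equally weighted weekly readings and a slope through zero. Week 12 carries 12²/(1² + … + 12²) = 144/650 = 22% of the weight. A 53% loss at that one point costs 0.53 × 0.22 = about 12% of the slope.

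**7. Test the replacement window, Days 79-85.** For Monday to Friday starters the Saturday is Day 83, 82, 81, 80 or 79, with mean 81. The present mean is (83 + 82 + 88 + 87 + 86)/5 = 85.2, so the reading moves about 4 days earlier. With a Day 85 visit, 0% fall after the last dose. With visits spread equally over allowed weekdays within ± 4 days, only Monday starters (2 of 7 allowed visit days) and Tuesday starters (1 of 6) can still be late: (2/7 + 1/6)/5 = 9%. A rule tied to the actual last-dose date removes that remainder.

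**The case against.** The strongest reply is that little turns on this. Home SVC is exploratory and tested without multiplicity adjustment (Protocol 8.4.4.4). The primary analysis uses centrally confirmed clinic SVC (SAP 7.5.1). That stands, and it limits the weight of the point.

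Several stronger readings are tempting and should be resisted:

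- *About 60% of patients are measured off drug.* A reader might infer this as fact. It needs even Monday-Friday starts, which the documents do not report, and it ignores the protocol's ± 1 day tolerance. Not every patient supplies a home value either: the device is used only in suitable regions, and SAP 7.9.3 says use varies.
- *The home endpoint loses half its effect.* That is one end of the range. It assumes effect proportional to concentration and concerns only the Week 12 change endpoint.
- *Clinic SVC is always on drug, so home is the odd one out.* Not so. Protocol 5.15 encourages patients who stop drug early to return for remaining visits, so their Week 12 clinic SVC can be off drug. The contrast holds for patients who complete planned dosing.

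The remedy also draws fair objections. A blanket last-dose cut-off would make the home analysis on-treatment only while early discontinuers stay in the clinic analysis, so the rule must be confined to completers of planned dosing. The SAP 7.9.3.1 pairing uses its own seven-day window, so editing Appendix B alone would not reach it. With the ± 1 day tolerance, a Friday starter could have two readings in Days 79-85 (Days 79 and 85) or none (Days 78 and 86).

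**Conclusion.** The defect is real and follows from the documents: applied as written, the SAP labels some planned post-treatment readings as Week 12. With a Day 85 visit and Saturday tests, this affects Wednesday, Thursday and Friday starters by 3, 2 and 1 days, and by up to 5 days if the visit moves within its window.

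The overall share is conditional on unreported start weekdays: 60% under even Monday-Friday starts, about 40-60% under the test tolerance or seven-day starts, and roughly 30-80% in the uneven mixes tried. The resulting dilution of the Week 12 home change lies between zero and roughly half. The home slope loses at most about 12% under the same extreme and the simplified weighting used above.

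The primary endpoint and the confirmatory testing sequence are untouched. The point is worth fixing because it is predictable and cheap to remove, not because it threatens the trial's main conclusion.

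**What to change.** 1. **SAP Appendix B:** set the home-SVC windows to Days 2-8 (Week 1), 9-15 (Week 2), and so on to 79-85 (Week 12), with later weeks following in the same way. Each holds exactly one Saturday whatever the start weekday.
2. **SAP 5.5.4:** exempt home SVC from the midpoint statement.
3. **Add a rule:** for patients who complete planned dosing, home readings after the date of last dose are post-treatment and are not used in analyses through Week 12. Name the home change and slope endpoints, the combined home-plus-clinic model and the home-clinic pairing. Patients who stop study drug early are handled as in the clinic SVC analysis.

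**Cost:** SAP text and one table; data collection does not change. The Week 12 home reading is on average about 4 days earlier, and windows are no longer centred on the clinic visit day. A large share of readings now labelled Week 12 (60% under even Monday-Friday starts) move to the following week's window.

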APPENDIX C. REGIONAL SITE POOLING FOR FAS

Pooled Site Number	Country	State/Province	Site Number	Patient Count	Sub-total of Patient Count
1	Australia	New South Wales	061078	3	20
1	Australia	New South Wales	061080	3	
1	Australia	Queensland	061079	8	
1	Australia	South Australia	061081	2	
1	Australia	Western Australia	061082	4	
2	Ireland	Dublin	353090	4	53
2	Netherlands	Utrecht	031089	11	
2	Spain	Madrid	034098	38	
3	Canada	Alberta	002065	13	49
3	Canada	Alberta	002068	10	
3	Canada	Ontario	002060	15	
3	Canada	Ontario	002070	2	
3	Canada	Ontario	002071	7	
3	Canada	Saskatchewan	002077	2	
4	Canada	Quebec	002061	35	52
4	Canada	Quebec	002063	6	
4	Canada	Quebec	002066	11	
5	United States	Arizona	001051	10	61
5	United States	California	001014	8	
5	United States	California	001016	5	
5	United States	California	001026	5	
5	United States	California	001054	8	
5	United States	Colorado	001019	9	
5	United States	Oregon	001013	8	
5	United States	Oregon	001050	4	
5	United States	Washington	001023	4	
6	United States	Illinois	001055	6	71
6	United States	Indiana	001043	3	
6	United States	Iowa	001030	4	
6	United States	Kansas	001003	2	
6	United States	Michigan	001036	9	
6	United States	Michigan	001046	10	
6	United States	Minnesota	001032	3	
6	United States	Minnesota	001059	4	
6	United States	Missouri	001005	2	
6	United States	Missouri	001033	3	
6	United States	Nebraska	001042	4	

Pooled Site Number	Country	State/Province	Site Number	Patient Count	Sub-total of Patient Count
6	United States	Ohio	001028	7	
6	United States	Ohio	001057	10	
6	United States	Wisconsin	001037	4	
7	United States	District of Columbia	001035	2	51
7	United States	Maryland	001008	13	
7	United States	Pennsylvania	001006	11	
7	United States	Pennsylvania	001015	3	
7	United States	Tennessee	001039	9	
7	United States	Virginia	001022	3	
7	United States	Virginia	001067	8	
7	United States	West Virginia	001004	2	
8	United States	Connecticut	001025	10	
8	United States	Massachusetts	001045	3	
8	United States	New York	001001	3	
8	United States	New York	001017	5	
8	United States	New York	001027	10	
8	United States	Vermont	001056	5	
9	United States	Florida	001011	9	65
9	United States	Florida	001012	9	
9	United States	Florida	001066	1	
9	United States	Florida	001068	4	
9	United States	Georgia	001040	1	
9	United States	North Carolina	001010	8	
9	United States	North Carolina	001021	10	
9	United States	North Carolina	001047	9	
9	United States	Texas	001007	2	
9	United States	Texas	001020	3	
9	United States	Texas	001041	9	

APPENDIX D. MSPLINE VALUE FOR CALCULATION OF PREDICTED SVC

Table: Mspline Value

Age (yrs)	Male	Female	Age (yrs)	Male	Female
18	0.147849088	0.135507529	50	-0.006647706	0.028303776
19	0.160315109	0.140628299	51	-0.014542406	0.020206649
20	0.167159394	0.143647414	52	-0.022604908	0.011905392
21	0.169722148	0.145330204	53	-0.030845244	0.00339698
22	0.16923214	0.146039097	54	-0.039274925	-0.005323975
23	0.166543254	0.145870185	55	-0.04790158	-0.014258162
24	0.162315681	0.144942845	56	-0.056735557	-0.023411261
25	0.157092735	0.143626724	57	-0.065782826	-0.032797239
26	0.151293448	0.142211366	58	-0.07504859	-0.042417299
27	0.145106883	0.140771596	59	-0.084531216	-0.052260185
28	0.138681964	0.13919976	60	-0.094214527	-0.062313185
29	0.132266867	0.137441293	61	-0.104078877	-0.072556666
30	0.125876212	0.135494281	62	-0.114093666	-0.082975133
31	0.119459845	0.133330256	63	-0.124218952	-0.093558031
32	0.113049003	0.130878076	64	-0.134413719	-0.104301259
33	0.106735805	0.12804587	65	-0.14465155	-0.115203896
34	0.100550635	0.124811373	66	-0.154914171	-0.126261624
35	0.094499318	0.121203564	67	-0.165181495	-0.137466925
36	0.088531508	0.117238065	68	-0.175439763	-0.148808471
37	0.082567889	0.112889589	69	-0.185681902	-0.160268368
38	0.076537303	0.108171834	70	-0.195901978	-0.171827557
39	0.070402479	0.103107309	71	-0.20609542	-0.183468534
40	0.064129074	0.097699941	72	-0.216260542	-0.195173143
41	0.057677943	0.091939589	73	-0.226393699	-0.206921242
42	0.051046568	0.085825419	74	-0.236485333	-0.218692812
43	0.04427255	0.079389589	75	-0.246523325	-0.230468005
44	0.037387387	0.07268763	76	-0.256496316	-0.242227571
45	0.030394993	0.06577409	77	-0.266395583	-0.253951742
46	0.023277783	0.058677615	78	-0.276212134	-0.265621352
47	0.01602077	0.051384134	79	-0.285939277	-0.277219902
48	0.008623361	0.043889005	80	-0.295573257	-0.288731661
49	0.001072775	0.036196648
